5.3.2 Serious Adverse Events (Immediately Reportable to the Sponsor)

All serious adverse events are required to be reported by the investigator to the Sponsor immediately (i.e., no more than 24 hours after learning of the event; see Section 5.5.2 for reporting instructions). A serious adverse event is any adverse event that meets any of the following criteria:

- Fatal (i.e., the adverse event actually causes or leads to death)
- Life threatening (i.e., the adverse event, in the view of the investigator, places the patient at immediate risk of death)
 - This does not include any adverse event that had it occurred in a more severe form or was allowed to continue might have caused death.
- Requires or prolongs inpatient hospitalization (see Section 5.4.6.10)
- Results in persistent or significant disability/incapacity (i.e., the adverse event results in substantial disruption of the patient's ability to conduct normal life functions)
- Congenital anomaly/birth defect in a neonate/infant born to a mother exposed to study drug
- Significant medical event in the investigator's judgment (e.g., may jeopardize the patient or may require medical/surgical intervention to prevent one of the outcomes listed above)

The terms "severe" and "serious" are not synonymous. Severity refers to the intensity of an adverse event (rated as mild, moderate, or severe or according to National Cancer Institute Common Terminology Criteria for Adverse Events [NCI CTCAE] criteria; see Section 5.4.4); the event itself may be of relatively minor medical significance (such as severe headache without any further findings).

Severity and seriousness need to be independently assessed for each adverse event recorded on the eCRF.

5.3.3 Adverse Events of Special Interest (Immediately Reportable to the Sponsor)

Adverse events of special interest are required to be reported by the investigator to the Sponsor immediately (i.e., no more than 24 hours after learning of the event; see Section 5.5.2 for reporting instructions). Adverse events of special interest for this study include the following:

- Cases of potential drug-induced liver injury that include an elevated ALT or AST in combination with either an elevated bilirubin or clinical jaundice, as defined by Hy's law (see Section 5.4.6.6)

- Suspected transmission of an infectious agent by etrolizumab as defined below:

Any organism, virus, or infectious particle (e.g., prion protein transmitting transmissible spongiform encephalopathy), pathogenic or non-pathogenic, is considered an infectious agent. A transmission of an infectious agent may be suspected from clinical symptoms or laboratory findings that indicate an infection in a patient exposed to a medicinal product. This term applies only when a contamination of the study drug is suspected.

- Adverse events of special interest specific to etrolizumab:

Systemic hypersensitivity reactions and anaphylactic and anaphylactoid reactions (see Section 5.1.1.2 and Sampson's Criteria in Appendix 9)

Neurological signs, symptoms, and adverse events that may suggest possible PML on the basis of a positive finding on the PML Subjective Checklist that is accompanied by a positive finding on the PML Objective Checklist or if there is strong clinical suspicion for PML (see Appendix 7 PML algorithm and Section 5.1.1.1.1, above)

5.4 METHODS AND TIMING FOR CAPTURING AND ASSESSING SAFETY PARAMETERS

5.4.1 Adverse Event Reporting Period for Part 1 (OLE)

After informed consent has been obtained, all adverse events, regardless of relationship to study drug, will be reported until the patient completes Part 1 (OLE).

During Part 1 (OLE), the investigator is responsible for ensuring that all adverse events (see Section 5.3.1 for definition) are recorded on the Adverse Event eCRF and reported to the Sponsor in accordance with instructions provided in this section and in Sections 5.5, 5.6, and 5.7. The investigator is also responsible for reporting medical device complaints (see Section 4.3.3.3).

For each adverse event recorded on the Adverse Event eCRF, the investigator will make an assessment of seriousness (see Section 5.3.2 for seriousness criteria), severity (see Section 5.4.4), and causality (see Section 5.4.5).

Investigators will seek information on adverse events at each patient contact. All adverse events, whether reported by the patient or noted by study personnel, will be recorded in the patient's medical record and on the Adverse Event eCRF. Past resolved adverse events will be recorded in the medical history according to their medical relevance. Adverse events reported ongoing at the end of the Phase II OLE or Phase III controlled studies will be stated unresolved in those studies and reopened in Study GA28951. The adverse event will be reported in Study GA28951 with the start date and adverse event term identical to those in the parent study (i.e., the Phase II OLE study or a Phase III controlled study). The severity (NCI CTCAE grade) should be evaluated by the investigator at the start of Part I (OLE) and recorded in the "AE initial NCI CTCAE grade" field of the Adverse Event eCRF for Study GA28951. The most extreme NCI CTCAE grade for the event should also be recorded, taking into account the severity of the event since it was first reported during the parent study.

Adverse events reported as ongoing at the end of Part 1 (OLE) (i.e., the end of the 12-week safety follow-up) will be recorded as unresolved.

Some patients may not enroll into Part 2 (SM), although all patients will be strongly encouraged to enter. For those patients who do not enroll into Part 2 (SM) (i.e., withdraw consent from the study), investigators are not required to actively monitor patients for adverse events after the patient completes the 12-week safety follow-up in Part 1 (OLE). However, if they become aware of any serious adverse events that are believed to be related to prior study drug treatment, these should be reported to the sponsor (see Section 5.7). In addition, the Sponsor should be notified if the investigator becomes aware of any post-study events of confirmed or suspected PML, regardless of relationship to study drug, for up to 2 years after the patient's last dose of study drug.

5.4.2 Adverse Event Reporting Period for Part 2 (SM)

Part 2 (SM) of the OLE-SM study is focused on extended follow-up for PML. During Part 2 (SM) the investigator will use the PML assessment interview to monitor for signs and symptoms of PML. The investigator is not required to actively monitor patients for other adverse events in Part 2 (SM); however, if he or she becomes aware of any other non-PML serious adverse events that are believed to be related to any prior study drug treatment, these should be reported to the Sponsor.

The investigator should report such events directly to Roche or its designee either by faxing or by scanning and emailing the Serious Adverse Event/Adverse Event of Special Interest Reporting form with use of the fax number or email address provided to investigators.

5.4.3 Eliciting Adverse Event Information in Part 1 (OLE)

A consistent methodology of non-directive questioning should be adopted for eliciting adverse event information at all patient evaluation timepoints. Examples of non-directive questions include the following:

“How have you felt since your last clinic visit?”

“Have you had any new or changed health problems since you were last here?”

5.4.4 Assessment of Severity of Adverse Events

The adverse event severity grading scale for the NCI CTCAE (Version 4.0) will be used for assessing adverse event severity. Table 3 will be used for assessing severity for adverse events that are not specifically listed in the NCI CTCAE.

Table 3 Adverse Event Severity Grading Scale for Events Not Specifically Listed in NCI CTCAE

Grade	Severity
1	Mild; asymptomatic or mild symptoms; clinical or diagnostic observations only; or intervention not indicated
2	Moderate; minimal, local, or non-invasive intervention indicated; or limiting age-appropriate instrumental activities of daily living ^a
3	Severe or medically significant, but not immediately life-threatening; hospitalization or prolongation of hospitalization indicated; disabling; or limiting self-care activities of daily living ^{b, c}
4	Life-threatening consequences or urgent intervention indicated ^d
5	Death related to adverse event ^d

NCI CTCAE = National Cancer Institute Common Terminology Criteria for Adverse Events.

Note: Based on the most recent version of NCI CTCAE (v4.0), which can be found at: http://ctep.cancer.gov/protocolDevelopment/electronic_applications/ctc.htm

- ^a Instrumental activities of daily living refer to preparing meals, shopping for groceries or clothes, using the telephone, managing money, etc.
- ^b Examples of self-care activities of daily living include bathing, dressing and undressing, feeding one's self, using the toilet, and taking medications, as performed by patients who are not bedridden.
- ^c If an event is assessed as a "significant medical event," it must be reported as a serious adverse event (see Section 5.5.2 for reporting instructions), per the definition of serious adverse event in Section 5.3.2.
- ^d Grade 4 and 5 events must be reported as serious adverse events (see Section 5.5.2 or reporting instructions), per the definition of serious adverse event in Section 5.3.2.

5.4.5 Assessment of Causality of Adverse Events

Investigators should use their knowledge of the patient, the circumstances surrounding the event, and an evaluation of any potential alternative causes to determine whether an adverse event is considered to be related to the study drug, indicating "yes" or "no" accordingly (see Table 4). The following guidance should be taken into consideration:

- Temporal relationship of event onset to the initiation of study drug
- Course of the event, considering especially the effects of dose reduction, discontinuation of study drug, or re-introduction of study drug (where applicable)
- Known association of the event with the study drug or with similar treatments
- Known association of the event with the disease under study
- Presence of risk factors in the patient or use of concomitant medications known to increase the occurrence of the event
- Presence of non-treatment-related factors that are known to be associated with the occurrence of the event

Table 4 Causal Attribution Guidance

Is the adverse event suspected to be caused by the study drug on the basis of facts, evidence, science-based rationales, and clinical judgment?	
YES	There is a plausible temporal relationship between the onset of the adverse event and administration of the study drug, and the adverse event cannot be readily explained by the patient's clinical state, intercurrent illness, or concomitant therapies; and/or the adverse event follows a known pattern of response to the study drug; and/or the adverse event abates or resolves upon discontinuation of the study drug or dose reduction and, if applicable, reappears upon re-challenge.
NO	Adverse events will be considered related, unless they fulfill the criteria as specified below. Evidence exists that the adverse event has an etiology other than the study drug (e.g., preexisting medical condition, underlying disease, intercurrent illness, or concomitant medication); and/or the adverse event has no plausible temporal relationship to administration of the study drug (e.g., cancer diagnosed two days after first dose of study drug).

5.4.6 Procedures for Recording Adverse Events

Investigators should use correct medical terminology/concepts when recording adverse events on the Adverse Event eCRF. Avoid colloquialisms and abbreviations.

Only one adverse event term should be recorded in the event field on the Adverse Event eCRF.

5.4.6.1 Diagnosis versus Signs and Symptoms Injection-Site Reactions

Local cutaneous adverse events that occur at or around the injection site during or within 24 hours after study drug injection should be captured separately as individual signs (e.g., erythema, induration/swelling at injection site) and symptoms (e.g., pain, pruritus at injection site) rather than a diagnosis of allergic reaction or injection-site reaction.

Other Adverse Events

For adverse events other than injection-site reactions, a diagnosis (if known) should be recorded on the Adverse Event eCRF rather than individual signs and symptoms (e.g., record only liver failure or hepatitis rather than jaundice, asterixis, and elevated transaminases). However, if a constellation of signs and/or symptoms cannot be medically characterized as a single diagnosis or syndrome at the time of reporting, each individual event should be recorded on the Adverse Event eCRF. If a diagnosis is subsequently established, all previously reported adverse events based on signs and symptoms should be nullified and replaced by one adverse event report based on the single diagnosis, with a starting date that corresponds to the starting date of the first symptom of the eventual diagnosis.

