1.3 OUTCOME MEASURES FOR GA28951 PART 1 (OLE)

1.3.1 Efficacy Outcome Measures

The efficacy outcome measures for this study are as follows:

- pMCS remission assessed at Weeks 0, 4, 8 and then in 12-week intervals during GA28951 Part 1 (OLE)
- MCS remission assessed at Week 108 during GA28951 Part 1 (OLE)
- Endoscopic remission at Week 108 during GA28951 Part 1 (OLE)

The efficacy outcome definitions are provided below:

Outcome Measure	Definition
Mayo Clinic Score (MCS)	MCS (0–12) is a composite of 4 assessments, each rated from 0-3: stool frequency, rectal bleeding, endoscopy, and PGA
Partial Mayo Clinic Score (pMCS)	pMCS (0–9) is a composite of 3 assessments, each rated from 0-3: stool frequency, rectal bleeding, and PGA

MCS Remission	MCS ≤ 2 with individual subscores ≤ 1 and a rectal bleeding subscore of 0
MCS Clinical Response	MCS with ≥ 3 -point decrease and 30% reduction from baseline as well as ≥ 1 -point decrease in rectal bleeding subscore or an absolute rectal bleeding score of 0 or 1
pMCS Remission	pMCS ≤ 2 , with, rectal bleeding score of 0, PGA 0–1 and stool frequency subscore 0–1
Improvement in endoscopic appearance of the mucosa	Endoscopy subscore ≤ 1
Endoscopic Remission	Endoscopy subscore = 0

ES= Endoscopic Subscore; PGA = Physician's Global Assessment.

Endoscopy Score=1 includes mild friability criteria unless identified in the description of an endpoint above.

1.3.2 **Safety Outcome Measures**

The safety outcome measures for GA28951 Part 1 (OLE) of this study are as follows:

- Incidence and severity of adverse events
- Incidence of serious adverse events
- Incidence, rate per subject-year, and severity of infection-related adverse events
- Incidence of serious infection-related adverse events
- Incidence and severity of injection-site reactions
- Incidence of adverse events leading to etrolizumab discontinuation
- Incidence of laboratory abnormalities
- Incidence and rate per subject-year of malignancies
- Incidence and severity of hypersensitivity reactions

1.3.3 **Exploratory Outcome Measures**

The exploratory outcome measures for GA28951 Part 1 (OLE) are as follows:

- Histologic appearance of mucosa at Week 108
- Incidence of ATAs to etrolizumab (*de-prioritised from a safety outcome measure. See Section 4.4 for details*)

Due to termination of study GA28951, exploratory outcome measures will **not** be reported in the Primary CSR.

1.4 **ANALYSIS TIMING**

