Summary tables will be generated for AEs, serious adverse events (SAEs), deaths, AEs leading to discontinuation of study drug, and AESIs. A listing will be generated for AEs, deaths, selected AESIs/specific AEs, and COVID-19 AEs. Pregnancies will be reported as narratives in the study CSR.

Summary tables of AEs will summarize the incidence of treatment-emergent AEs only. Treatment-emergent events are defined as any new AE reported on or after the first dose of OLE study drug or any worsening of an existing condition. Note that worsening of existing conditions include AEs ongoing from the UC parent studies (GA28948, GA28949, GA28950, GA29102, and GA29103). Otherwise, only AEs reported on or after the first dose of OLE study drug are included. If the onset date of the AE is prior to

the day of first dose, the AE will be considered treatment emergent only if the most extreme intensity is greater than the initial intensity (i.e., the intensity for a given AE increases and its end date is on or after the date of the first dose). For all summary tables, the AEs will be sorted by SOC (in decreasing order of overall incidence) and then by preferred term (PT) (in decreasing order of overall incidence).

For OLE etrolizumab treatment, the incidence count for each AE PT will be defined as the number of patients reporting at least one treatment-emergent occurrence of the event (multiple occurrences of the same AE in 1 patient will be counted only once). The proportion of patients with an AE will be calculated as the incidence count divided by the total number of patients in the population. Each table will also present the total number of AEs reported where multiple occurrences of the same AE in an individual are counted separately.

Rate tables will be generated for selected AEs of interest. The rate per 100 patient years and 95% CIs will be summarized by treatment group and will be calculated by:

$$\begin{aligned} & \text{AE Rate (per 100 patient years)} \\ &= \frac{\text{Total number of AEs (in OLE only)}}{\text{Total number of patient years at risk (in OLE only)}} \times 100 \end{aligned}$$

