where the total patient-years at risk is the sum over all patients of the time intervals (in years) from the first dose of study treatment in Part 1 (OLE) until the patient completes/withdraws from the study (including the 12-week safety follow-up, if applicable). Only treatment emergent AEs with an onset date after the first dose of open label etrolizumab in GA28951 will be included within these outputs.

All summary tables and listings will report AEs using the OLE population.

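### A malignancy diagnosed in Part 1 that replaces a symptom carried over from the parent study takes a pre-OLE onset and is always left out of the malignancy rate

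*Protocol*

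**What the plan says.** Five rules act together.

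- **Dating a diagnosis (Protocol 5.4.6.1).** For events other than injection-site reactions, once a diagnosis is established, the symptom events are voided and a single event takes their place, "with a starting date that corresponds to the starting date of the first symptom of the eventual diagnosis".
- **Events ongoing at rollover (Protocol 5.4.1; also 4.4.1.1).** These are left unresolved in the parent study and reopened here: "The adverse event will be reported in Study GA28951 with the start date and adverse event term identical to those in the parent study".
- **Incidence tables (SAP 4.2.2).** A new event counts if reported on or after the first OLE dose. If its onset is earlier, "the AE will be considered treatment emergent only if the most extreme intensity is greater than the initial intensity".
- **Rate tables (SAP 4.2.2).** "Only treatment emergent AEs with an onset date after the first dose of open label etrolizumab in GA28951 will be included within these outputs". There is no exception for worsening or for the date of diagnosis.
- **Rate denominator (SAP 4.2.2).** Each patient contributes all time from the first OLE dose to completion or withdrawal, with the 12-week safety follow-up where it applies.

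The malignancy rate is a named Part 1 safety outcome in SAP 1.3.2: "Incidence and rate per subject-year of malignancies".

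**The concern.** Each rule is ordinary in a stand-alone trial. In a rollover study, the recorded onset of a diagnosis can fall in a different study from the diagnosis itself. The parent study closes with an unresolved symptom. The cancer is then recognised in GA28951, but its recorded onset lies before the window that the GA28951 rate covers. The exclusion for malignancy (Protocol 4.1.2) applies to patients who developed one during the parent study. It does not cover a patient who enters with an early symptom not yet diagnosed.

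Compared with a count by date of diagnosis, the effect can only lower the rate: events leave the numerator and no person-time leaves the denominator. Long-term safety is a stated Part 1 objective. Malignancy counts are likely to be low, so a single case can visibly change the rate.

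**Working it through.** The plan states no expected malignancy rate, event count or patient-years, so there is no figure of its own to reproduce. The check has two parts.

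**1. Applying the rules to one case.** Suppose a symptom was reported as an adverse event 30 days before the first OLE dose and was still ongoing at rollover. It is diagnosed as a malignancy on OLE day 200. Protocol 5.4.1 reopens the symptom with onset at day −30. Protocol 5.4.6.1 replaces it with the malignancy, also dated day −30. The SAP 4.2.2 rules then give the first two rows below. The last two rows are for comparison.

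| Recorded onset | Grade | Incidence table | Rate table |
|---|---|---|---|
| Before first OLE dose | no rise | out | out |
| Before first OLE dose | rises | in | out |
| Day of first OLE dose | any | in | out, if *after* is read strictly |
| Date of diagnosis in the OLE | any | in | in |

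A back-dated malignancy is out of the rate in both of its rows. Whether it reaches the incidence table depends on its initial grade. For a carried-over event, the investigator grades severity at the start of Part 1 (Protocol 5.4.6.3). No section says whether a replacement diagnosis inherits that grade or starts with its own. The third row arises because SAP 4.2.2 uses *on or after* the first dose to define treatment emergence but *after* it for the rate tables.

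**2. Effect on the rate.** The SAP formula is 100 × events / patient-years. Let n malignancies be diagnosed in Part 1, k of them back-dated before the OLE, over T patient-years.

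- Counted by diagnosis: 100 × n / T
- As the SAP counts: 100 × (n − k) / T
- Relative shortfall: k / n, whatever T is

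Illustration, with n, k and T all assumed and exact Poisson 95% intervals, for n = 10 and T = 4,000:

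- k = 0: 100 × 10 / 4,000 = 0.25 per 100 patient-years (0.12 to 0.46)
- k = 1: 100 × 9 / 4,000 = 0.225 (0.10 to 0.43), 10% lower
- k = 3: 100 × 7 / 4,000 = 0.175 (0.07 to 0.36), 30% lower

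With T = 2,000 and n = 10, the rate by diagnosis is 0.50, falling to 0.45 (k = 1) or 0.35 (k = 3). With T = 8,000 it is 0.125, falling to about 0.11 or 0.09. With n = 20 and k = 1, the shortfall is 1/20 = 5%. In all these cases the shift is small beside the width of the interval, but its direction is fixed.

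**The case against.** **The route is narrow.** This stands. It is explicit only for a symptom that was reported as an adverse event, was ongoing at rollover and was later absorbed into the diagnosis. Symptoms that resolved earlier go to medical history, and the text does not say whether they count as the first symptom. Protocol 5.4.6.2 asks for separate events when association is unclear. Protocol 5.4.6.9 makes anticipated UC symptoms adverse events only if they worsen unexpectedly, so a symptom put down to colitis may leave no earlier event to replace. Protocol 5.4.1 also keeps the reopened term identical to the parent study's, which sits uneasily with replacing it; the start date is pre-OLE either way.

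**First-symptom dating is defensible.** This also stands. Many patients come from placebo, adalimumab or infliximab. For them, disease already symptomatic before OLE Day 1 began before any etrolizumab exposure. Table 4 of the protocol gives a cancer diagnosed two days after the first dose as an example of an implausible temporal relationship. A reader might infer that the onset-based rate is wrong and should be replaced. The documents do not support that: the two dates answer different questions, and each has a cost.

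**The cases are not hidden.** This is partly right. Malignancies are reported as specific adverse events, and SAP 4.2.2 provides for listings of adverse events. A listing does not change the reported rate, however, and nothing marks which cases were diagnosed in the OLE but dated earlier.

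**Infections.** A reader might extend the point to infection rates as a material bias. The documents do not support this. An ongoing serious infection must resolve, with anti-infective treatment finished, before dosing (Protocol 4.1.2 and 5.1.1.1.2). Only an undiagnosed infection symptom that persists across rollover would follow this route.

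**Conclusion.** The point holds for malignancies on the route described: a symptom reported as an adverse event, ongoing at rollover, and replaced in Part 1 by the diagnosis. Such a case is excluded from a named rate outcome in every reading of SAP 4.2.2, and no section dates it by diagnosis. The shortfall against a count by diagnosis is k/n.

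It is tempting to turn this into a number of lost cases. The documents give no malignancy rate, no Part 1 patient-years and no share of back-dated diagnoses. The figure of about 2100 is a maximum for the whole study, including patients who enter Part 2 only. Any such count would return its own assumptions, and the illustration above shows scale only. Nor can it be said that these cases belong to no rate anywhere, because the parent-study analysis plans are not available here.

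This is a small, one-directional gap in a safety outcome where counts are likely to be low. It is worth closing because closing it is cheap.

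**What to change.** In SAP 4.2.2:

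1. Keep the onset-based malignancy rate as planned.
2. Add a supplementary rate and a listing of malignancies first diagnosed, or first reported as that diagnosis, after the first OLE dose, whatever the recorded onset. Show onset and diagnosis or first-report date side by side. Where they can be identified, list serious or opportunistic infections in the same way.
3. Identify these cases from existing data: the date an event became serious (Protocol 5.4.6.3), the EDC audit trail (Protocol 7.1) and case narratives.
4. Use either *after* or *on or after* the first dose in both the treatment-emergence definition and the rate tables, or explain the difference.

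No new eCRF field is proposed. The sponsor terminated Part 1 on 15 February 2022, with last dosing on 15 May 2022, and a synoptic report is planned. Retrospective collection across sites would be out of proportion.

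The cost is a modest amount of extra analysis and case review. The supplementary rate may count some disease that was already symptomatic before the OLE, and it should be labelled accordingly. Reading it beside the onset-based rate shows how much the dating rule matters.
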